Interventions to Promote Healthy Lifestyle and Academic Performance in Children During the Summer Months.

NCT03321071

June 4th, 2020

Methods

Trial Design

This study is a three-armed quasi-experimental study employing a repeated measure within and between participant design comparing the HSL (n=60), to 21C (n=60), and no program (n=60). HSL is designed to mitigate academic learning loss and accelerated summer BMI gain by positively impacting children's obesogenic behaviors.

Participants

To distribute the costs of operating HSL the study takes place over two summers (i.e., June-August, 2018 & 2019). A single elementary school in the Columbia, SC metropolitan area will participate each summer (i.e., two schools, one each summer). Schools will be selected because they serve children from low-income households (100% free and reduced priced lunch) and they operate a 21C summer program. Inclusion criteria are that children are in the 2nd, 3rd, or 4th grade and their standardized reading score on the Measures of Academic Progress is between the 25th and the 75th percentile. Exclusion criteria is the presence of a severe intellectual disability (e.g., fragile X syndrome, severe autism). Measures of Academic Progress scores between the 25th and the 75th percentile and the absence of a severe intellectual disability were chosen as inclusion/exclusion criteria because these are the criteria the school district used to select children to participate in the 21C. A total of 90 students will participate each summer (i.e., 180 participants total). Participants will be assigned to one of three conditions HSL (n=60), 21C (n=60), or no program (n=60).

Interventions

HSL was designed in partnership with the local school district in which the study will occur. HSL was designed to, (1) address summer declines in reading achievement and (2) mitigate accelerated unhealthy weight gain during the summer by positively impacting children's obesogenic behaviors. HSL will operate at the participating schools and will be delivered by certified teachers. Participants enrolled in HSL will attend daily (Monday-Thursday, 8:00-15:30) for six weeks during the summer, with a one-week break in the middle of the program (i.e., 4th of July). The program day will consist of alternating sixty-minute periods of physical activity (3

total hours) with one hour and forty-five-minute periods of reading instruction (3.25 total hours). All participants will be provided a United States Department of Agriculture (USDA) Summer Feeding Program compliant breakfast (8:00-8:30), lunch (12:30-13:00), and a healthy snack. The USDA Summer Feeding Program mandates that foods align with the meal patterns laid out by this program. For breakfast this includes the provision of both fruits and vegetables and whole grain options and excluding sugar-sweetened milk beverages. In addition, breakfasts cannot exceed 500 kcal, 10% kcal from saturated fat, and 430 mg of sodium and lunches will not exceed 650 kcal, 10% kcal from saturated fat, and 640 mg of sodium. Lunches are required to include milk, fruits and/or vegetables, a grain, and a meat or meat alternative. For snacks the program could choose two of the four components of the lunch guidelines and had to include a fruit or vegetable. A 15-minute nutrition education session, based on the USDA Team Nutrition Curriculum [1], will be delivered by one of the teachers each day during lunch. The USDA Team Nutrition Curriculum focuses on eating a variety of low-fat foods and incorporating fruits, vegetables, and whole grains into children's diets daily. Nutrition Education sessions typically consisted of a 5-minute lesson by a certified teacher followed by a 10-minute activity session (e.g., activity sheets, comic book readings).

The 21C is a federally funded program providing academic enrichment opportunities for students who attend low-performing schools. Students enrolled in 21C will attend the same school as children enrolled in HSL. The 21C will operate daily (Monday-Thursday) from 8:30-14:00 for four weeks during the summer. The program day will consist of academic sessions in the morning and afternoon (9:00-11:30 & 12:30-13:45) and one hour of physical activity before lunch (11:30-12:30). All participants will be provided a USDA Summer Feeding Program compliant breakfast (8:30-9:00) and lunch (11:30-12:30). Children in the control will not attend either program.

Outcomes

For Body Mass Index Measures of Academic Progress Reading Scores and Cardiorespiratory Fitness baseline data collection will be conducted during the last month of the school year prior to the intervention summer.

Follow-up assessments will be conducted 3-months following baseline. For Physical Activity, Sleep, Screen Time, and Diet measures will be collected continuously from baseline to outcome.

Body Mass Index – Primary Outcome. Following standardized protocols trained research assistants will collect children's heights (nearest 0.1 cm) and weights (nearest 0.01 lbs.) without shoes in light clothing using a portable stadiometer (Model S100, Ayrton Corp., Prior Lake, Minn.) and digital scale (Healthometer model 500KL, Health o meter, McCook, Ill.). BMI will be calculated ($BMI = \text{kg}/\text{m}^2$) and transformed into age and sex specific z-scores (zBMI) according to the Centers for Disease Control growth charts [2].

Measures of Academic Progress Reading Scores – Primary Outcome. Children's reading achievement will be assessed via the MAP reading assessment. Created by the Northwest Evaluation Association (www.nwea.org), MAP results are widely accepted and used extensively in school-aged children [3]. Scores are reported using the Rasch Unit Scale, a curriculum scale developed using Item Response Theory that estimates student achievement. The Rasch Unit Scale ranges from 140-300 and are norm referenced based on grade [3]. MAP reading assessment will be administered as part of typical curriculum in the fall (first month of school) and end of the spring (last month of school) of each year.

Cardiorespiratory Fitness – Secondary Outcome. The Progressive Aerobic Cardiovascular Endurance Run (PACER) will be administered during regularly scheduled PE [4-10]. The PACER will be carried out by a trained research assistant and the PE teacher following standardized protocols on a marked outdoor green space.

Physical Activity & Sleep – Physical activity (MVPA, sedentary time) and sleep (total sleep duration, sleep onset, sleep offset, midpoint) will be measured using a Fitbit Charge 2TM (Fitbit Inc., San Francisco, California, USA). Fitbit Charge 2 devices have demonstrated initial reliability and validity for detecting heartrate and sleep [11-13]. Each Fitbit will be assigned a unique numeric identifier and each device will be linked to Fitabase (San Diego, CA, USA) a web-based interface that allows remote access and download of participants' second level

Fitbit data. Children will be asked to wear the Fitbit device every day for the entire summer (i.e., 12 weeks) starting the last week of school in the spring (May) until the first week of school in fall (August). Parents will be sent text reminders to sync and charge their child's Fitbit device every 3-4 days. Only days with >10 hours of waking wear [14] will be considered valid. Data processing will be informed by the ISCOLE data processing protocols [14].

Consistent with previous studies [15-18], daily resting heartrate for each child will be distilled into activity intensity levels by identifying the average of the lowest 10-mins beats-per-minute during wake time for each day. Resting heartrates above the 95th (90bpm), or below the 5th (50bpm) percentile will be considered implausible and replaced with the closest day that the child had a plausible resting heartrate. Percent heart rate reserve (HRR) will be calculated using the following formula
$$\frac{\text{heart rate}-\text{resting heart rate}}{\text{maximum heart rate}-\text{resting heart rate}}$$
 and will be used to determine activity intensity levels, with 0.0-19.9% of HRR as sedentary, and $\geq 50.0\%$ as MVPA.²⁸⁻²⁹ Maximum heart rate was defined as 197 beats per minute for all children [19]. Sleep will be identified and parsed from activity.

Sleep onset will be defined as the first minute that the sleep episode began. Sleep offset will be selected as the last minute that a sleep episode was recorded. The sum of the minutes that the Fitbit device classifies a child as asleep during a sleep episode will be considered total sleep time. Only nocturnal sleep will be considered for this study and will be defined as sleep onset that occurred between 5pm and 6am and lasted for greater than 240 minutes [20]. Sleep segments separated by less than 20 minutes will be considered one continuous sleep segment.

Screen Time and Diet

Parents will complete the following measures through an online survey that will be texted to their smartphone twice per week (i.e., one weekday and one weekend day) during the 12-week period that children wear the Fitbit device and will be encouraged to discuss their estimates with children to improve accuracy.

Parents will be asked to estimate the total amount of time (hours and minutes) their child spends in front of a screen taht day (e.g., TV, computer, video game, smartphone, and tablet).

Diet will be assessed via parent report food screener[21]. Items will be scored by four possible response categories and responses consist of the following: 0 ('child did not consume'), 1 ('child consumed a little'), 2 ('child consumed some'), and 3 ('child consumed a lot') with those individual items. Individual food items will be grouped in accordance with the Healthy Meal Index (HMI) [22]. Food categories include; fruits, vegetables, dairy (non-sugar based), convenience foods, sweets and desserts and sugar sweetened beverages. Consumption will be dichotomized (i.e., 'did' vs. 'did not' consume) and reported as mean days/week [21]. Two variables will be created for analysis of diet; healthy foods/drinks (fruits, vegetables, and dairy), unhealthy foods/drinks (convenience foods, and sweets/desserts, sugar sweetened beverages).

Sample Size

The above selection criteria will yield 60 children in each arm of the study. Previous studies have shown that samples of 60-100 participants provide reliable estimates of statistical and recruitment parameters upon which subsequent large-scale trials can be based [23].

Randomization

A total of 180 children will be randomly selected to participate in the study. Of the 180 children, 60 will be enrolled in 21C program. Children will not randomly assigned to the 21C program as the participating school declined random assignment of these children. The remaining 120 (i.e., n=60 in 2018 and n=60 in 2019) will randomly allocated to one of two conditions HSL or control (no program) using a random number generator. Random assignment will be completed by the study principal investigator who will not be involved in data collection and will be completed each summer after participants enrolled in the study using the runiform command in Stata (v14.2, College Station, TX). Once implemented randomization cannot be changed.

Data Analysis

All analyses will be completed using Stata (v14.2, College Station, TX) with α levels set to $P < 0.05$. Data will be assessed for normality and descriptive statistics of programs, child characteristics, and outcome variables at baseline. The analyses will be estimated using an intent-to-treat approach [24, 25]. Multilevel mixed effects linear regressions with measures nested within children will be estimated. Separate models will be estimated for each dependent variable and included dummed group (control, HSL, 21C), time (baseline, post-summer, post schoolyear), and all group-x-time interactions. All analyses will include baseline scores on the dependent variable, age, gender, race, and year of participation as covariates in the models. Missing data will be handled using full information maximum likelihood estimates [26, 27]. The Benjamini-Hochberg procedure with a false discovery rate of 10% will be utilized to account for multiple comparisons [28].

1. *The Effect of Nutrition Education on Third Graders' School Lunch Consumption in a School Offering Food Pyramid Choice Menus.* 1998. p. 34.
2. Kuczmarski, R., et al., *CDC growth charts for the US: methods and development.* Vital Health Stat, 2002. **11**(246): p. 1-190.
3. Thum Y. M. and C.H. Hauser, *NWEA 2015 MAP Norms for Student and School Achievement Status and Growth*, in *NWEA Research Report*. 2015, NWEA: Portland, OR.
4. Welk, G. and M.D. Meredith, *Fitnessgram and Activitygram Test Administration Manual-Updated 4th Edition*. 2010: Human Kinetics.
5. Tomkinson, G.R., et al., *Secular trends in the performance of children and adolescents (1980–2000)*. Sports Medicine, 2003. **33**(4): p. 285-300.
6. Beets, M.W. and K.H. Pitetti, *One-mile run/walk and body mass index of an ethnically diverse sample of youth*. Medicine and Science in Sports and Exercise, 2004. **36**(10): p. 1796-1803.
7. Beets, M.W. and K.H. Pitetti, *A Comparison of 20-M Shuttle-Run Performance of us Midwestern Youth to Their National and International Counterparts*. Pediatric Exercise Science, 2004. **16**(2): p. 94-112.
8. Beets, M.W., K.H. Pitetti, and B.J. Cardinal, *Progressive aerobic cardiovascular endurance run and body mass index among an ethnically diverse sample of 10-15-year-olds*. Research Quarterly for Exercise and Sport, 2005. **76**(4): p. 389-397.

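### The preceding fall's MAP reading score is routinely produced but left out of the reading analysis; adding it would give the randomised HSL-control comparison a modest, cheap gain in precision

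*Combined protocol and SAP*

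**What the plan says.** MAP reading is one of two primary outcomes. Under Outcomes, "MAP reading assessment will be administered as part of typical curriculum in the fall (first month of school) and end of the spring" of each year. For MAP, BMI and fitness, "baseline data collection will be conducted during the last month of the school year prior to the intervention summer", and "Follow-up assessments will be conducted 3-months following baseline". So the spring test is the only pre-program score and the next fall's test is the first outcome.

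Under Data Analysis, the mixed model has dummy-coded group, "time (baseline, post-summer, post schoolyear), and all group-x-time interactions". On adjustment: "All analyses will include baseline scores on the dependent variable, age, gender, race, and year of participation as covariates in the models". The preceding fall's MAP score is neither a time level nor a covariate.

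Under Participants, a child is eligible if "their standardized reading score on the Measures of Academic Progress is between the 25th and the 75th percentile". The band was adopted because "these are the criteria the school district used to select children to participate in the 21C". The administration that supplies the eligibility score is not named.

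Under Sample Size, "The above selection criteria will yield 60 children in each arm of the study". No power, effect size or SD is given. Under Randomization, HSL and control are randomised and 21C is not.

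**The concern.** A single test score carries measurement error. A second pre-program score on the same scale helps to average that error out, and so explains more of the variation in post-summer reading. Here the testing schedule produces that score without any new assessment. With 60 children per arm and no power calculation, precision on a primary outcome is worth having. For scale, an unadjusted comparison of 60 with 60 at two-sided 0.05 (sidedness is assumed) has 80% power for a difference of 0.51 SD.

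The unnamed eligibility test raises a second issue. If the spring score both selected the children and serves as their baseline, children from schools below the norm will have been picked partly for favourable error. Their next score would then tend to fall in every arm without any true loss. The program aims to address summer declines in reading, and the design is described as both within and between participants, so such a fall could be misread.

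**Working it through.** **Stated figures.** The plan gives no precision or power figure for MAP, so there is none to reproduce. The counts agree: 3 × 60 = 2 × 90 = 60 + 120 = 180.

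**Inputs.** From the documents: 60 per arm, the testing schedule, the covariates and the band. All correlations, variances and school means below are assumptions.

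**1. Precision from correlations.** Let r_s = corr(spring, post), r_f = corr(fall, post) and r_fs = corr(fall, spring). Residual variance with the spring score alone is 1 − r_s². With both scores it is 1 − (r_s² + r_f² − 2·r_s·r_f·r_fs)/(1 − r_fs²). With r_s = r_fs = 0.8, the spring score alone leaves 1 − 0.64 = 0.36.

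| r_f | Residual variance, both scores | Reduction |
|---|---|---|
| 0.80 (all equal) | 1 − 1.28/1.8 = 0.289 | 20% |
| 0.75 | 1 − 0.2425/0.36 = 0.326 | 9% |
| 0.70 | 1 − 0.234/0.36 = 0.350 | 3% |
| 0.64 (AR(1)) | 1 − 0.2304/0.36 = 0.360 | 0% |

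In the equal-correlation case, 60 per arm acts like 60/0.802 ≈ 75. With all correlations equal at 0.6, 0.7 and 0.9 the reduction is 14%, 17% and 22%.

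**2. Precision from a latent-trait model.** Fall = ability + error. Spring adds a school-year drift, and post adds a summer change. Assumed SDs in RIT points: ability 10-15, error 3-5, drift 3-5, summer change 3-4. The reduction is C²/(V·R), where C = cov(fall, post | spring), V = var(fall | spring) and R = var(post | spring).

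- Largest gain (SDs 15, 5, 3, 3): C = 225 − 225 × 234/259 = 21.72; V = 250 − 225²/259 = 54.54; R = 268 − 234²/259 = 56.59. Reduction = 471.7/(54.54 × 56.59) = 15.3%.
- Smallest gain (SDs 10, 3, 5, 4): C = 100 − 100 × 125/134 = 6.72; V = 109 − 100²/134 = 34.37; R = 150 − 125²/134 = 33.40. Reduction = 45.1/(34.37 × 33.40) = 3.9%.

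Selection on the spring score leaves the distribution of the other scores given spring unchanged, so the range stays at about 4-15%. Selection on the fall score restricts the fall score itself, and the range becomes about 1-7%. Overall, 60 per arm acts like about 61 (60/0.986) to 71 (60/0.847).

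**3. How the score enters.** With complete data, the group-by-time estimate is the difference between arms in mean change. A child-level covariate without a time interaction cancels from it. Three simulated example fits of a two-time-point version of the planned model confirmed this. Adding fall MAP as a main effect left the estimate unchanged (0.1290, 0.0022 and 0.0744 before and after) and lowered only the model SE (in the first, from 0.1102 to 0.1053). In 3,000 simulated trials (all correlations 0.8, band on spring, school at the norm), the SD of the HSL-control estimate was 0.1105 with an ANCOVA on spring and 0.0988 with spring and fall. With the band on fall it was 0.1003 and 0.0977.

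**4. Regression to the mean within an arm.** If spring is both the eligibility test and the baseline, the expected change is −(1 − r) × (mean score within the band − school mean). School SD is taken equal to the norm SD.

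- School at the norm: 0.
- 0.3 SD below: −(1 − 0.90) × 0.257 = −0.026 SD.
- 0.5 SD below: −(1 − 0.80) × 0.429 = −0.086 SD.
- 0.7 SD below: −(1 − 0.75) × 0.601 = −0.150 SD.

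If the preceding fall score set eligibility, the shift from spring to post is 0 under equal correlations. Under AR(1) with r = 0.7-0.9 it is −0.04 to −0.09 SD at 0.5 SD below the norm. In the simulations the mean HSL-control difference was within 0.002 of zero, as randomisation implies.

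**The case against.** Adjusting for a single baseline score is ordinary practice. The gain rests on correlations that the documents do not give, and it vanishes under AR(1) decay. The sample size is justified only as enough to estimate parameters for later trials, so the extra precision is an efficiency rather than the repair of an error. All of this stands, and it is why the gain is called modest. Exact AR(1) decay is a limiting case, however: measurement error in the spring score leaves independent information in the fall score.

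It is also fair that a fall score for every child is inferred from the testing schedule. A standard mixed model drops children with a missing covariate, so the planned likelihood estimation does not by itself cover them.

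Three stronger readings are tempting but unsupported.

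- A reader might infer that the percentile band makes a second pre-score worth more by narrowing the range. It does not: the gain is unchanged if the band was set on spring and smaller if it was set on fall.
- A reader might infer that regression to the mean biases the reading result. It cancels in expectation between HSL and control, and no section states a plan to interpret a within-arm fall as summer loss.
- A reader might want eligibility moved to the fall score. The band is the district's own 21C rule, so a different test for the randomised arms could make eligibility differ from 21C. The document is also dated June 2020, after both intervention summers.

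**Conclusion.** The point holds as a modest missed efficiency on a primary outcome. The documents describe a routinely produced earlier pre-score, and the analysis does not use it. Under the assumed inputs, including it in a suitable model reduces the residual variance of the randomised HSL-control comparison by roughly 1-15%, with outer limits of about 0 and about 20%. It adds no bias to that contrast.

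The secondary point is one of reporting and is conditional. If the spring test set the band and the schools lie 0.3-0.7 SD below the norm, with a test correlation of 0.75-0.90, about 0.03-0.15 SD of a within-arm decline is regression to the mean. At the norm it is zero. Adding the fall score as a covariate does not remove it from within-arm change.

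**What to change.** Obtain the preceding fall's MAP score from the school records. For the randomised HSL-control comparison of post-summer MAP, pre-specify one of two forms:

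- an ANCOVA of the post-summer score on both pre-scores, each with its own slope, plus the planned covariates and a stated method for missing fall scores; or
- a repeated-measures model with the fall score as an earlier time point, unstructured covariance, and HSL and control means constrained equal at both pre-program times. Under likelihood estimation this form also handles children without a fall score.

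Do not add the score only as a main effect in the planned group-by-time model.

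State which MAP administration set the eligibility band. Unless it is shown that the spring test did not, or that the schools lie at the norm, add that within-arm spring-to-fall change will not be interpreted as summer loss.

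The cost is one extra data item per child, possible missing fall scores for some children, a small change of model form for this outcome, and a few sentences in the analysis plan.

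### Replacing every daily resting heart rate outside 50–90 bpm biases MVPA and sedentary time for children whose usual rate truly lies outside those limits; how many such children there are is unknown

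*Combined protocol and SAP*

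**What the plan says.** All of this is in the Outcomes section of the combined protocol and SAP, under Physical Activity & Sleep.

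- Each child gets one resting rate per day, obtained by "identifying the average of the lowest 10-mins beats-per-minute during wake time for each day".
- Screening and replacement: "Resting heartrates above the 95th (90bpm), or below the 5th (50bpm) percentile will be considered implausible and replaced with the closest day" on which that child's value was in range.
- The resting rate enters the percent heart rate reserve (%HRR) formula, which "will be used to determine activity intensity levels, with 0.0-19.9% of HRR as sedentary" and 50% or more as MVPA.
- "Maximum heart rate was defined as 197 beats per minute for all children".

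The plan does not say whose percentiles these are (the study's child-days, its children, or an outside reference). It gives no artefact test, no rule for a child without an in-range day, and no sensitivity analysis of the replacement.

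**The concern.** A percentile limit flags values by rank. A child who stably runs at 95 bpm is treated exactly like a child whose sensor misread for one day. For the second child, borrowing a nearby day is reasonable. For the first, the only available donors are that child's own lowest days, so the substitute is always too low; for a child who stably runs below 50 it is always too high.

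%HRR is the only stated basis for MVPA and sedentary time, so an error in resting rate passes straight into both. Because it has the same sign on every day for that child, averaging over the 12 weeks does not remove it. What is at stake is the accuracy of two behavioural outcomes through which the HSL programme is meant to act. The plan labels them neither primary nor secondary.

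**Working it through.** **Inputs from the plan:** limits 50 and 90 bpm, described as the 5th and 95th percentiles; maximum heart rate 197; sedentary 0.0–19.9% and MVPA at least 50% of HRR; 180 children; 12 weeks (84 days). The plan states no percentage replaced, so there is no figure to reproduce.

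**1. Share replaced.** If the percentiles are those of the study's daily values: 5% + 5% = 10%, or at most 0.10 × 180 × 84 = 1,512 of 15,120 child-days before the wear rule. If 50 and 90 come from elsewhere, the share depends on the children studied. For an assumed normal distribution it is about 1% with mean 70 and SD 8, and about 16% with mean 80 and SD 10.

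**2. Effect on the cut-points.** A cut at fraction f of HRR lies at RHR + f(197 − RHR) bpm, where RHR is the resting rate.

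- Sedentary (f = 0.2): 0.8 × RHR + 39.4
- MVPA (f = 0.5): 0.5 × RHR + 98.5

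An error of d bpm in RHR moves these by 0.8d and 0.5d.

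| True → assigned RHR | Sedentary cut (bpm) | MVPA cut (bpm) |
|---|---|---|
| 95 → 90 | 115.4 → 111.4 | 146.0 → 143.5 |
| 100 → 85 | 119.4 → 107.4 | 148.5 → 141.0 |
| 45 → 50 | 75.4 → 79.4 | 121.0 → 123.5 |

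**3. Direction.** This step needs no distributional assumption. After processing, every value lies in 50–90. A child whose usual rate is above 90 therefore has every assigned value below that rate: both cuts are too low, MVPA is overstated and sedentary time understated. For a child usually below 50, both cuts are too high and MVPA is understated. In addition, minutes below the substituted rate have negative %HRR, and the stated sedentary band starts at 0.0%.

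**4. Size, by simulation.** Assumptions: daily values normal with 5th and 95th percentiles at 50 and 90, so mean 70 and SD 40/(2 × 1.645) = 12.16; 60 days per child (84 gives nearly the same); replacement by the nearest in-range day. The between-child share of variance is not in the documents, so it is varied. Error is the mean absolute difference from the child's own mean on flagged days.

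| Between-child share | Children of 180 with at least half their days replaced | Children of 180 with no donor day | Error (bpm), raw → replaced |
|---|---|---|---|
| 0.3 | under 1 | 0 | – |
| 0.5 | about 4 | 0 | about 12.7 → 6.3 |
| 0.7 | about 9 | about 0.1 | about 8 → 6 |
| 0.8 | about 12 | about 0.5 | about 6.0 → 5.6 |
| 0.9 | 15 to 16 | about 2 | about 3.6 → 4.7 |

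For children whose own mean exceeds 90, the assigned rate is about 9 bpm too low at a share of 0.5 and about 6 bpm too low at 0.9. Under the same model, the child's own median would be within about 1.1 bpm (share 0.5) to 0.5 bpm (share 0.9) of the child's mean on those flagged days.

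**5. In minutes.** Assume 13 waking hours (780 min) and heart rate above resting following a gamma distribution with mean 25 and SD 18.

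- True 96 assigned 89: sedentary time falls from 378 to 259 min and MVPA rises from 71 to 89 min.
- True 96 assigned 86: sedentary time falls to 204 min and MVPA rises to 97 min. A 10 bpm error is just beyond the simulated 6–9 bpm.
- True 45 assigned 55, also a 10 bpm error: about 155 min per day have negative %HRR and belong to no stated band.

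**The case against.** The strongest counter-argument is that the rule often helps. If a child has a stable underlying rate and the daily values scatter around it, replacing an extreme day brings the value closer to the child's own mean at variance shares up to about 0.8; only near 0.9 does it make matters worse (table above). At low and moderate shares most replaced days belong to children whose usual rate is in range. This stands, so it would be wrong to infer that the rule degrades the data overall. It does not rescue the minority whose usual rate is outside the limits, and a child-referenced screen handles both groups better.

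Other objections also stand:

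- **The 10% is conditional.** A reader might take it as fixed by the word percentile. The plan never names the reference distribution, so it is not.
- **The average effect is small.** Over all child-days in the model, treating each daily value as true, MVPA shifts by about 2 min per day or less on about 33. Sedentary time shifts by about 7 min or less on about 470 if negative %HRR counts as sedentary, or up to about 21 min on the literal bands. The error is large only for particular children.
- **Negative %HRR is partly a separate wording gap.** The resting rate is an average of the lowest 10 minutes, so some minutes fall below it without any replacement. Upward substitution enlarges the gap.

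Two stronger readings are not supported. One is that the arms are biased differently, through changes in fitness or in quiet waking time. The rule is the same in every arm, the models adjust for baseline score and nest measures within children (which would partly absorb a stable offset), and nothing in the documents shows a differential effect. The other is that the rule destroys the study's cardiac data. The plan describes downloading second-level device data and nowhere says raw values are discarded; it is only silent about keeping a flag.

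**Conclusion.** The concern holds in limited form. The plan overwrites resting rates on rank alone. For any child whose usual rate is truly outside 50–90 bpm, the resulting error in MVPA has a known sign and does not average out, and the sedentary band is incomplete below 0%. That much follows from the plan's own formula. The handling of a child with no in-range day is undefined.

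The size is uncertain. The figures of 6–9 bpm and 4–16 of 180 children rest on an assumed normal distribution matched to 50 and 90 and an assumed between-child share of 0.5–0.9; at 0.3 fewer than one child in 180 is heavily affected. The documents do not show how many flagged values are true and how many are artefact. zBMI and MAP reading, the primary outcomes, do not depend on this rule. It is worth correcting because the correction is cheap, not because a main conclusion is at risk.

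**What to change.** 1. Replace the group-percentile screen with a child-referenced one. Take the median of the child's daily values over valid-wear days, either as that child's resting rate or as the reference for screening daily values. Set aside a daily value only if it departs from that median by more than an amount stated in advance. Every child with valid-wear days then has a value, which closes the no-donor gap.
2. Define sedentary as %HRR below 20%, including negative values.
3. Report the number of values changed, by arm.
4. Repeat the MVPA and sedentary-time analyses with the 50/90 rule and with no replacement, as sensitivity analyses. For the 50/90 version, state where the percentiles come from and how a child with no in-range day is handled.

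The cost is processing code on data the plan already downloads, a short change to the SAP text, and two extra runs of the activity models. The drawback is that a single child-level rate ignores real drift in resting rate over the 12 weeks; using the median only as a screening reference avoids most of that.

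### Does surveying screen time and diet on one weekday and one weekend day per week distort the group effects?

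*Combined protocol and SAP*

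**What the plan says.** Under Outcomes, Screen Time and Diet, parents answer a texted survey "twice per week (i.e., one weekday and one weekend day") for the 12 weeks of Fitbit wear. The screen-time item asks about that day only. Diet items are reduced to consumed or not consumed and "reported as mean days/week". No rule is given for turning two sampled days into a weekly figure.

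The opening of Outcomes lists these measures with activity and sleep: "Diet measures will be collected continuously from baseline to outcome". The wear window runs "starting the last week of school in the spring (May) until the first week of school in fall (August").

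Under Interventions, "Participants enrolled in HSL will attend daily (Monday-Thursday, 8:00-15:30) for six weeks during the summer", with a one-week break. 21C also runs Monday to Thursday, for four weeks.

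Data Analysis gives one model form for every outcome: measures nested within children, group, "time (baseline, post-summer, post schoolyear), and all group-x-time interactions". It adds: "All analyses will include baseline scores on the dependent variable, age, gender, race, and year of participation as covariates in the models". Day type does not appear, and no weights are mentioned.

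**The concern.** The programs act directly on Monday to Thursday only, while half of the scheduled reports come from Saturday or Sunday. A mixed model fitted to all reports without weights estimates an effect for a half-weekend mix of days. If the programs change behaviour mainly on the days children attend, that effect is smaller than the effect over an ordinary week.

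This could matter for two reasons. HSL is meant to work through obesogenic behaviours, so the size of the screen-time and diet effects bears on its rationale. Sample Size also justifies the numbers by estimates for later, larger trials, so effect sizes count as well as significance. In addition, the time levels have no during-summer category, so it is unclear where the program-week surveys go.

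**Working it through.** The plan states no weekend weight and no effect size for these outcomes, so there is no figure to reproduce.

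**Scheduled records.** 12 weeks × 2 = 24 per child, 12 of them on weekends. The weekend share is 12/24 = 1/2, against 2/7 of the calendar. Weekends are over-weighted by (1/2)/(2/7) = 1.75 and weekdays under-weighted by (1/2)/(5/7) = 0.70. This comes from the 1:1 sampling without weights. The missing during-summer level plays no part in it.

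**Where the surveys enter.** Program weeks supply 6 × 2 = 12 of 24 surveys in HSL and 4 × 2 = 8 of 24 in 21C (counting the HSL break week as outside the six). The model's levels are baseline, post-summer and post schoolyear. If only the first and last survey weeks feed the first two (an assumption), 2 × 2 = 4 of 24 surveys are used. Those are school weeks, so few if any program days enter and the weighting question largely disappears. The window closes in August, so no survey can fill the post-schoolyear level. The model sentence is generic, and analysts must adapt it for these outcomes in any case.

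**Size if program-week surveys are pooled.** Let f be the effect on non-program days divided by the effect on program days. The documents do not give f; the range 0 to 1 is assumed. With equal response and survey weekdays spread over Monday to Friday, the share of program days is 0.5 × 4/5 = 0.4 of records and 4/7 of days:

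ratio of pooled to seven-day effect = (0.4 + 0.6f) / (4/7 + 3f/7)

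| f | ratio | understatement |
|---|---|---|
| 0 | 0.700 | 30% |
| 0.25 | 0.811 | 19% |
| 0.5 | 0.891 | 11% |
| 1 | 1.000 | 0% |

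- If the survey weekday is always Monday to Thursday, the f = 0 ratio is 0.5/(4/7) = 0.875, a 12.5% understatement.
- If weekday reports are a share w of completed reports, the f = 0 understatement is 1 − 0.8w/(4/7): 44% at w = 0.40, 16% at 0.60 and 0% at 5/7. Response rates are not given.
- If behaviour rebounds on non-program days, f is negative and the gap grows. At f = −0.25 the ratio is 0.25/0.464 = 0.54.

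**Check by simulation.** A random-intercept model was fitted to 120 simulated children in two arms, with six weeks and two reports a week. The assumed effect was −40 on weekdays and 0 on weekends. The pooled contrast was −19.5 (expected −20). Combining day-specific contrasts 5/7 and 2/7 gave −28.1 (expected −28.6). Adding day type as a main effect left the contrast at −19.5, so adding that term alone would not alter the estimate.

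**Cost of reweighting.** With equal day-level variances the standard error changes by √{[(5/7)² + (2/7)²]/0.5} = √1.184 = 1.088. With intraclass correlation r and n records per child the factor is √{[r + 1.184(1 − r)/n]/[r + (1 − r)/n]}. For n = 12 this is 1.039 at r = 0.1 and 1.007 at r = 0.5 (both values of r assumed). Reweighting loses signal to noise once 1/ratio falls below the factor. Within program weeks that happens above f = 0.61 at 1.088, 0.80 at 1.039 and 0.96 at 1.007.

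**Diet scale.** Suppose consumption on 50% of weekdays and 70% of weekend days (assumed). Simple averaging gives 7 × (0.5 + 0.7)/2 = 4.2 days a week; the seven-day value is 5 × 0.5 + 2 × 0.7 = 3.9. The shift of 0.3 is one of level, and cancels between arms if it is common to them.

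**The case for a change.** The strongest case for a change is that both readings of the plan leave something unsettled. Pool the program-week surveys and the effect refers to a half-weekend mix. Use only the ends of the window and 20 of 24 surveys go unused, including those from the weeks when the programs run. For diet, a weekly frequency is the plan's own scale, and a plain average of the two days does not produce it. A few sentences would settle this with no new data, provided survey dates are stored, which the documents do not say.

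The gap in description stands: neither the mapping of surveys to time levels nor the conversion to days per week is written down. The claim of bias does not. It needs a pooling step that the plan does not describe, a seven-day target that the plan does not state for screen time, and an f well below 1. For diet, nothing shows that simple averaging is intended, and f near 1 is plausible because the nutrition lessons are aimed at daily eating.

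**Conclusion.** No change is needed. Two things remain, and neither is an error.

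The first is missing detail. Anyone analysing these outcomes must decide which surveys represent each time level and how two days become a weekly frequency. Sensible answers are available, such as a during-summer level and five times the weekday proportion plus twice the weekend proportion.

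The second is a trade-off. An equal weekday/weekend contrast and a calendar-week contrast are both defensible. Under unweighted pooling the first is smaller by 0% to 30% for f between 1 and 0, given equal response and survey weekdays spread over Monday to Friday. Moving to the second costs up to about 9% in standard error, less with within-child correlation, and loses signal to noise when effects carry over to other days.

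If a program has no effect on any day, the contrast is zero under either weighting, so the null test is unaffected. This assumes the arms have the same weekday share among completed reports. BMI and the reading scores, the two primary outcomes, are untouched, and screen time and diet are labelled neither primary nor secondary.
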